Patient dose has been determined by the least radiation dose from the radiopharmaceutical that will provide enough counts in the tomograph detectors to obtain quantifiable images with adequate counting statistics. The exposure of the patient to the radiopharmaceutical will only be until the radioactive label decays. The half life of fluorine-18 is 109.8 minutes. Maximum duration of radiation exposure is therefore limited by this half-life. The number of doses administered is determined by the number of PET/CT scans required by the study protocol. The total effective dose will not exceed reasonably safe limits set by the FDA as described in the investigator's brochure for 18F-choline. Each dose of 18F-choline is administered intravenously as a single unit dose. A radioactivity dose of 0.09 millicuries per kilogram of body weight will be prescribed and obtained from the cyclotron laboratory. A dose calibrator in the PET imaging suite will be used to confirm the actual dose to be administered. Only a dose falling within a 10% range of the calculated prescribed dose will be administered.

I.6. Observations and Measurements to Fulfill the Objectives of the Study

Source documents (clinical, radiographic, and pathology reports), obtained from the medical record (office or hospital) following subject written informed consent, will be abstracted to generate a list of known sites of active disease. A table of these sites for each subject will be entered into a password-protected database.

I.7 Investigational Observations and Measurements to Fulfill the Objectives of the Study

The 18F- Choline injection is infused into the subject intravenously over 1 minute. The PET scanning is started approximately 10 minutes after the start of infusion. PET imaging data, from the neck to the proximal femur is then collected. PET data is analyzed by: a) visual assessment, and b) semi-quantitative region of interest (ROI) analysis. Standardized uptake values (SUV) will be recorded from each ROI. Implicit in the definition of SUV is the requirement that the tomograph be properly calibrated so that activity in tissue can be determined in uCi/ml. Structural imaging (CT, MRI) when available will be used for anatomical correlation. If a PET/CT scan is performed, the CT performed for attenuation correction will provide some anatomical correlation data. The PET/CT imaging protocol is described in section I.10.

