Research involving human subjects is covered by federal law and institutional policies. All research conducted at our institution requires review and pre-approval by a Scientific Review Committee followed by approval from an Institutional Review Board. Subjects will be given a Queen's Medical Center IRB-approved consent.

I.10. PET/CT Protocol

Instrument: Gemini TF-64 PET/CT (Philips Medical Systems N.A., Bothell, WA)

Scan Protocol: Low-Dose CT, Liver PET Protocol

Isotope Dose: 18F-Fluoromethylcholine, **0.09 mCi/kg** patient body weight on day of scan.

1. A copy of the signed consent form will be faxed to the Research Regulatory Office.
 2. Height, sex, and age of the patient are recorded. Body weight, blood pressure, pulse, temperature and respiratory rate are obtained. The obtained weight is used to determine 18F-choline dose.
 3. Using sterile technique, an intravenous catheter is inserted by a trained IV technician into an arm vein. The catheters are flushed with sterile saline. The patient is placed in the supine position on the scanning table.
 4. A vial of 18F-choline containing a dose of 0.09 mCi/kg of body weight will be obtained from the cyclotron laboratory. A dose calibrator in the PET imaging suite will be used to confirm the actual administration dose. Only a dose falling within a 10% range of the calculated prescribed dose will be administered.
 5. A topographic scan will be performed to identify anatomical boundaries and the axial imaging field of view. The field of view is to encompass the liver, with 1cm margin from the upper limit of the field.
 6. A CT transmission scan in the supine position is acquired over the upper abdomen. The 64-channel helical CT scanning parameters were: 120 kV, 30-50 mA/slice, rotation time 0.75 sec, slice thickness/interval 5.0mm. No intravenous contrast will be used with CT.
 7. The 18F-choline is injected by bolus followed by a 10 cc saline flush. Image acquisition is begun immedi-
-

ately with the flush in a dynamic mode using the following timing schema:

Frame #	Duration (seconds)
1-20	10
21-23	40
24-27	120
28-30	240
31	360

However, if it is determined in the initial 5 subjects that the dynamic imaging data fits well into a 1-tissue kinetic model of FCH uptake where activity levels eventually plateau or become linear, then the dynamic scan can be shortened (to 12-15 minutes, for example) and the dynamic frames curtailed accordingly.

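### Protocol I.10 step 7 starts the dynamic scan at the saline flush, an unstated interval after tracer injection begins; starting at injection would remove a conditional truncation risk at almost no cost

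*Protocol*

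**What the plan says.** Section I.10, step 7 (Protocol) gives the order of events: "The 18F-choline is injected by bolus followed by a 10 cc saline flush". Image acquisition then begins at once "with the flush in a dynamic mode using the following timing schema". The schema has 31 frames, of which the first twenty last 10 s each. I.10 does not say how long the injection takes or how much time separates its start from the start of the scan.

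The same step names a kinetic analysis. If in the first 5 subjects "the dynamic imaging data fits well into a 1-tissue kinetic model of FCH uptake", with activity that levels off or becomes linear, the dynamic scan may be shortened for later subjects.

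Step 5 sets the imaging region: "The field of view is to encompass the liver, with 1cm margin from the upper limit of the field". The protocol describes no blood sampling during the scan and does not say where an input curve would come from.

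The only administration time in the protocol is in section I.7: "The 18F- Choline injection is infused into the subject intravenously over 1 minute". I.7 pairs it with a different scan start: "The PET scanning is started approximately 10 minutes after the start of infusion". I.7 also refers the reader to I.10 for the imaging protocol.

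**The concern.** A 1-tissue model relates the tissue curve to an input curve, and its uptake rate constant (K1) depends heavily on the first minutes of both. With no blood sampling described, the images are the only visible source of the input. Twenty 10 s frames at the start look designed to follow tracer arrival, although the protocol does not say so.

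Step 7 opens frame 1 when the flush begins, which is after the tracer has been pushed. If the push takes longer than the journey from arm vein to liver, some tracer arrives before the scanner is running, and that part of the input cannot be recovered. A fit that treats the input as starting at frame 1 then has too little input for the tissue activity it sees, and K1 comes out too high. The fit in the first 5 subjects governs whether later scans may be shortened, so an avoidable timing artefact could enter that decision.

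**Working it through.** The protocol gives no figure for this point, so there is none to reproduce.

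**Inputs from the protocol**
- Frame schema (I.10, step 7): 20 × 10 s, 3 × 40 s, 4 × 120 s, 3 × 240 s, 1 × 360 s.
- Trigger (I.10, step 7): acquisition starts with the flush.
- Administration time: none in I.10; 1 minute in I.7.
- Half-life of fluorine-18 (I.5): 109.8 minutes.

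**Assumptions**
- D, the time from start of injection to start of flush: 3 to 60 s. Only 60 s has a source in the protocol (I.7).
- t, the transit time from arm vein to field of view: 8 to 25 s.

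**Step 1: the schema.** 200 + 120 + 480 + 720 + 360 = 1880 s, or 31.3 minutes. The 10 s frames cover the first 200 s.

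**Step 2: input lost before frame 1.** Tracer reaches the field of view t seconds after injection starts and the scan opens at D, so the loss is max(0, D − t).

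| D (s) | Loss at t = 8 s | Loss at t = 25 s |
|---|---|---|
| 3 to 5 | 0 | 0 |
| 10 | 2 | 0 |
| 20 | 12 | 0 |
| 30 | 22 | 5 |
| 60 | 52 | 35 |

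**Step 3: what truncation does to K1.** This is a noise-free illustration with an assumed input shape (a dispersed first pass plus a recirculating tail), K1 = 0.9 per minute and a washout constant k2 = 0.03 per minute. Input before the scan start was set to zero, and the model was refitted to the 31 frame means, weighted by frame duration.

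| D (s) | t (s) | Share of the first 200 s of input lost | K1 bias |
|---|---|---|---|
| 3 to 10 | 8 to 20 | at most 0.1% | at most 0.1% |
| 20 | 8 | 8.3% | +8.1% |
| 20 | 15 | 1.0% | +0.9% |
| 20 | 20 | 0.0% | 0.0% |
| 60 | 8 | 40.2% | +50.0% |
| 60 | 15 | 33.0% | +37.5% |
| 60 | 20 | 28.0% | +29.8% |

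The percentages depend on the assumed curve. The pattern does not: no bias without truncation, and an upward bias that grows with it.

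**Step 4: a shift of time zero without truncation.** Let the input be C(s) and the tissue curve K1 ∫ C(u) exp(−k2(s − u)) du. If C is zero before D, moving the clock origin to D moves both curves by the same amount and leaves K1 and k2 unchanged. Decay over the offset is small: 1 − 2^(−10/6588) = 0.1% for 10 s and 0.6% for 60 s, where 6588 s = 109.8 × 60.

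**Step 5: after the change.** If acquisition opens at the start of injection, the loss is max(0, 0 − t) = 0 for every D. Even at D = 60 s and t = 25 s, the last of the injected tracer first reaches the field of view at about 85 s, well inside the 200 s of 10 s frames.

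**The case against.** The strongest reply is that step 7 specifies a bolus, and for a bolus the harm vanishes. Steps 2 and 3 bear this out: up to about 10 s, the loss is 0 to 2 s and the bias is negligible. This stands.

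The second reply is that the large figures combine two procedures that the protocol never combines. I.7 pairs its 1-minute infusion with a scan start about 10 minutes later, not with a flush-triggered start, and it refers to I.10 for the imaging protocol. This also stands. The 35 to 52 s figure describes what would follow if the two sections were mixed; no stated procedure produces it. The 30 s case has no source in the documents and only illustrates the range.

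Third, no passage mentions an input curve or gives the purpose of the 10 s frames. I.7 names visual assessment and region-of-interest uptake values, and the kinetic model appears only in the condition for shortening the scan. The purpose is therefore an inference. It is a reasonable one, because a 1-tissue fit needs an input and uptake values do not need twenty 10 s frames.

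A reader might infer three stronger things that the documents do not support:
- *That the early rise is being lost.* This needs an administration longer than the transit time, and I.10 gives neither.
- *That a time zero differing between patients itself biases the rate constants.* It does not when input and tissue curves come from the same frames (step 4). Only truncation does.
- *That the loss varies by patient and injection times go unrecorded.* Any loss would vary with the length of the push as well as with the patient's transit time, and neither is stated. Step 9 mentions a flow sheet whose contents are not shown, so the protocol is silent on recording.

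What remains is that the trigger refers to the wrong end of the injection for a kinetic study, and no interval is fixed.

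**Conclusion.** The point holds as a conditional weakness in a stated rule. Step 7 ties the scan start to the flush and leaves the interval from the start of injection open. On the assumed transit times of 8 to 25 s, the cost is essentially nil for a bolus of up to about 10 s, 0 to 12 s of input at 20 s, 5 to 22 s at 30 s, and 35 to 52 s if I.7's 1 minute were used with this trigger. The corresponding illustrative K1 bias, for transit times of 8 to 20 s, is about 0% up to 10 s, 0 to +8% at 20 s, and +30 to +50% at 60 s.

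This rests on assumed injection and transit times, an assumed input shape, and the inference that the input would be taken from the images. Severity is low. The reason to act is that missed early frames cannot be recovered, while the change is nearly free and works whichever administration statement survives reconciliation.

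**What to change.** In I.10, step 7:
- Start the dynamic acquisition at, or a few seconds before, the start of tracer injection, with the flush following while the scanner runs.
- Count frames from the start of injection.
- Record the clock times of injection start, injection end and flush start for each subject.

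Reconcile the statements on administration and scan start in I.7 and I.10. Which of them is right is for the investigators to decide; this change alters only the scanner trigger, not the dose or the rate of injection.

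The cost is one reworded step, three recorded times and a few seconds of extra acquisition. If the schema keeps its length, the scan ends earlier relative to injection by the administration time, at most 60/1880 = 3.2% of the schema for a 1-minute administration. For subjects already scanned, any known offset should be noted with the data.

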Appendix: Standard Operating Procedures for Collection of Tumor and Liver Tissue Specimens

1.0 Scope and Applicability

This standard operating procedure (SOP) describes the methods for tissue sample collection, preparation, storage, and reporting.

2.0 Definition

2.1 Research Subject Information and Consent Form: This is the signed document allowing consent (i.e., Chain of Custody records), by the patient and surgeon. This document must be available before or during the surgical procedure before the patient is included into his study. A Photo copy of the document must be available at the Queen's Medical Center, Hawaii Medical Center Pathology laboratory and the Cancer Research Center oh Hawai'I (CRCH).

2.2 Surplus Tissue: Tissue normally discarded by the pathology lab. This material will be designated by pathology personnel and retained by Cancer Research Center of Hawaii personnel.

3.0 Cautions

3.1 Tissue samples must be handled expediently and properly, as the tissue quality will be adversely affected by prolonged transport time or changes in temperature.

3.2 To minimize the potential for cross-contamination of samples, sterile technique and use of sterile equipment or sterilized instruments will be available through Cancer Research Center of Hawaii personnel.

1. Sterile gloves, Derm Assist, size 7.5, R.Weinstein #132750, 50 pairs per box
2. Sterile gloves, Triflex, size 7.5, Cardinal #2D7254, 40 pairs/box
3. Sterile gauze, ProAdvantage, 4 x 4, R.Weinstein #P157025, 25 x2 /package
4. Sterilized forceps, VWR, 6" round tip dissecting, 82027-378, pack of 12
5. Sterilized knife handle, Cardinal #4781, each.
6. Sterilized Autopsy Knife Blade, Cardinal, #4783, each.

4.0 Responsibilities

4.1 Surgical staff (Surgical Associates office [name]) is responsible for identifying potentially eligible cases and notifying CRCH lab ([name]) of patient's surgical date and time.

4.2 CRCH is responsible for notifying the pathology laboratory ([name]) of the surgery and preparing instrument sterilization and supplies. CRCH is also responsible for coordinating and monitoring tissue sample collection, transportation and providing technical assistance as needed.

4.3 Pathology Lab is responsible for receiving and analyzing the tissue samples, and aliquoting a portion of the desired entity to CRCH.

5.0 Apparatus and Materials

- 5.1 Gloves, sterile **
- 5.2 Gauze, sterile**
- 5.3 Forceps, dissecting, sterilized**
- 5.4 Knife handle for Autopsy knife blade, sterilized**
- 5.5 Knife blade, autopsy, disposable, sterilized**
- 5.6 Cooler, Igloo transport, with three (3) sterile specimen containers and ice*
- 5.7 Specimen ID Labels, preprinted*
- 5.8 Specimen Accession sheet*
- 5.9 Zip-lock Bags*
- 5.10 Surgical blades, sterile*
- 5.11 Cryogenic storage Boxes*
- 5.12 Allprotect, Qiagen, #76405 or RNA Later*
- 5.13 Formalin*

** Item will be used by hospital

. * Item will be used by CRCH.

6.0 Procedure

6.1 Sample Collection Criteria:

6.1.1. Any fresh surgical tissue from human liver samples that have been identified by surgeon.

6.1.2. Tissue selection based on (1) representative histology from primary site, (2) correspondence to a specific area on PET/CT if identified by radiologist, (3) minimal necrosis, (4) sufficient residual tissue to constitute Surplus tissue requirement. Biopsy samples should not be selected unless the pathology lab has approved its availability.

6.1.3. At minimum, two 0.5 cm cubes, one of tumor and one of normal tissue are requested.

6.2 Sample Preparation:

6.2.1 Surgical team will deliver fresh, specimen to Pathology lab.

6.2.2 Gloves must be worn when handling or cutting liver sections.

6.2.3 **Use a new, sterilized, disposable autopsy blade and forcep** to minimize the potential for RNA contamination of samples. Sections for CRCH should be taken using “Sterile Technique.”

6.2.4 At minimum, two core cubes are requested. For large tumors (> 5 cm greatest diam.), multiple tumor and normal specimens will be collected and numbered A1, A2 etc:

- **Section A for tumor** – Minimum 0.5 cm. cube. Label as “Sample _A”
- **Section B for normal, adjacent** – 0.5 cm cube. Label as “Sample _B”
- **Sections C or more** – 0.5 cm.cube. Label as “Samples C,” etc. May be substituted as necessary.
- **Section for non-liver** – No sections, unless directed by the P.I., surgeon, or pathologist.

6.2.5 All sections should be labeled and provided a discrete accession sequence under the CRCH numbering scheme. Record each sample description on the **Specimen Accession Form**, as approved by Pathology.

6.3 Documentation/Reporting:

6.3.1 CRCH will retrieve the subject’s tissue sample from HMC and process the tissue sample according to the SOP.

6.3.2 The specimen IDs are pre-printed and labels will be attached to the **Specimen Accession Form**. ID labels are meant to be placed on the sterile specimen container at the time of collection.

6.3.3 The CRCH number must be recorded on the signed **Research Subject Information and Consent Form**. Please review the form for the appropriate signatures. Incomplete forms will be rejected, and no tissue collection will be done.

6.3.4 Record the information requested on the **Specimen Accession Form**. Please write or Addressograph:

- 6.3.4.1 Patient name,
- 6.3.4.2 Physician,
- 6.3.4.3 Surgical procedure,
- 6.3.4.4 Surgery date,
- 6.3.4.5 Surgery time,
- 6.3.4.6 Patient Consent Form, yes or no,
- 6.3.4.7 Time delivered to pathology lab
- 6.3.4.8 Date and time of pick-up
- 6.3.4.9 Initials of person doing pick-up

If the pre- or post-operation diagnosis is available, please indicate them under “Relevant Information.” Please write legibly and provide remarks for each sample if needed with any issues or concerns.

6.3.5 **One sample per accession**(i.e., Do Not mark more than one site per entry.) The Specimen Accession Form must be filled.

6.3.6 A finalized copy of the surgical report is requested. This may be either faxed or mailed to:
[name]
[name]
[name]
[contact]

6.4 Transporting Fresh tissue to CRCH:

6.4.1 Prepare ice chips or cool packs. Depending on the number of samples to be transported, the cool chest is hard sided and contains enough ice to cool tissues, but not freeze. Study staff should put the cool packs in a refrigerator or standard freezer. (**Note: Do not put the cool packs in the -80 C freezer**).

6.4.2 Put sterile specimen containers (6) in transport cool chest. Also, one zip-lock bag, gallon sized.

6.5 Handling and Storage.

6.5.1 Liver samples will be cut using a sterile technique into 4 equal parts:

6.5.1.1 RNA Later, stored in -20c

6.5.1.2 Allprotect, stored in -80c

6.5.1.3 Cryovial storage, stored in liquid nitrogen

6.5.1.4 Formalin fixation, followed within 24 hours by tissue processing. All excess tissue given will be processed, rather than discarded.

6.5.2 Sections will be accessioned onto a CRCH database and the exact locations of the different samples will be plotted.

7 Procedure

7.1 Surgical Associates ([name]) will notify CRCH Lab ([name]) of surgical scheduling of a prospective participant. This must include:

7.1.1 Patient identifier.

7.1.2 Surgical date.

7.1.3 Surgical time.

7.2 CRCH lab will notify pathology lab of the scheduling.

7.3 CRCH will arrange transportation and supplies for the surgical collection.

7.4 On the day of the surgery, surgery staff ([name]) will notify CRCH within 30 minutes of expected dissection.

7.5 The pathology receives and dissects specimen. Instruments and tools will be handled by CRCH lab.

7.6 CRCH transports the tissue specimens back to CRCH

7.7 CRCH further dissects the specimen into the following components

7.7.1 DNA, RNA, and protein

7.7.1.1 Allprotect or RNA Later

7.7.2 Cryopreservation, Snap freezing into liquid nitrogen

7.7.3 Fresh frozen paraffin embedded (FFPE), permanent storage

8.0 Records

8.1 CRCH will secure and retain all pertinent records as required by HIPAA.

9.0 Quality Control and Quality Assurance

9.1 To ensure tissue sample/data quality, CRCH will monitor the tissue sample collection process. If sample quality or any processing issues occur, CRCH will modify the SOP and notify all offices and/or labs involved to resolve any problems or issues.

10.0 Reference:

N/A
